65 The data from the ITT cohort will be analyzed according to the group to which the participants
66 were assigned through randomization, regardless of treatment actually received.

67 A per-protocol analysis will be performed to provide additional information regarding the
68 magnitude of the treatment effect. The per-protocol analysis will only be performed if more than
69 10% of randomized participants would be excluded by these criteria (e.g., 13 or more
70 participants if exactly 124 are enrolled).

71 The ITT analysis is considered the primary analysis. If the results of the per-protocol and ITT
72 analyses give inconsistent results, then the per-protocol analysis will be interpreted with caution.
73 In this scenario, exploratory analyses will be performed to evaluate possible factors contributing
74 to the differences.

75 **1.4 Analysis of the Primary Efficacy Outcome**

76 The primary outcome of central VMT release without rescue treatment at 24 weeks is a binary
77 variable that is graded by the central reading center. Logistic regression will be used to test the
78 hypothesis of superiority. The risk difference for the treatment group effect (estimated with
79 conditional standardization)⁴, along with the 95% confidence interval (estimated with the delta
80 method)⁴ and *P* value will be used to compare treatment groups. To aid in interpretation of the
81 risk difference, observed outcome proportions will be reported for each treatment group.

82 Since the chance of re-attachment after release before 24 weeks is highly unlikely, an eye with
83 central VMT release without rescue treatment prior to 24 weeks will be considered to have met
84 the outcome through 24 weeks if the participant is lost to follow-up. Similarly, any eye receiving
85 rescue treatment prior to 24 weeks will be considered not to have met the outcome through 24
86 weeks.

87 Multiple imputation will be used to impute missing data for eyes lost to follow-up that did not
88 have prior release or rescue treatment documented. The imputation model will treatment group,
89 and VMT status at 1, 4, 12, and 24 weeks.

90 A sensitivity analysis will be conducted using the same approach as above, but without multiple
91 imputation (i.e., complete-case analysis).

92 **1.5 Analysis of the Secondary and Exploratory Efficacy Outcomes**

93 The ITT analysis cohort will be used for all secondary and exploratory outcomes.

94 **1.5.1 Secondary Efficacy Outcomes**

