195 Secondary subgroup analyses will include ERM presence at the site of vitreous adhesion, lens
196 status (phakic or pseudophakic), retinoschisis, subretinal fluid within the central 1 mm, length of
197 adhesion on OCT (less than or equal to 1500 microns or greater than 1500 microns), and diabetes
198 status (has diabetes or does not have diabetes). Subgroups will be defined by the value at
199 baseline.

200 There are no data to suggest that the treatment effect will vary by sex or race/ethnicity. However,
201 both of these factors will be evaluated in exploratory subgroup analyses as mandated by National
202 Institutes of Health (NIH) guidelines.

203 Subgroup factors will be analyzed as categorical and continuous or ordinal variables where
204 possible. Secondary and exploratory subgroup analyses will only be conducted if there are at
205 least 20 eyes in each subgroup for each treatment group. The primary subgroup analysis will be
206 conducted regardless of sample size.

207 **1.12 Multiple Testing**

208 There will be no formal adjustment for multiple testing. Only $P \leq .05$ will be considered of
209 interest.

210 **1.13 Visit Windows for Analysis**

211 The analysis windows for visits will be defined according to Table 1. If multiple visits fall within
212 the same window, priority will be given to the protocol visit over unspecified visits. If there is no
213 protocol visit in the window, then the visit closest to the target date (but within the analysis
214 window) will be designated as the analysis visit. Visit windows will be filled in the following
215 order to handle visits occurring on the border of two windows: 24 weeks, 12 weeks, 4 weeks, 1
216 week.

217 **Table 1. Analysis Windows**

Visit \pm Protocol Window	Target	Analysis Window
1 week (-4 days to +3 days)	7 days	1 day – 2 weeks (1 – 14 days)
4 (± 1) weeks	28 days	2 – 8 weeks (14 – 56 days)
12 (± 2) weeks	84 days	8 – 18 weeks (56 – 126 days)
24 (± 4) weeks	168 days	18 – 40 weeks (126 – 280 days)

218 **1.14 Missing Data**

219 The strategy for handling missing data generally is included with the description of each
220 analysis. For analyses using multiple imputation, the Markov chain Monte Carlo (MCMC)
221 method with 100 imputations will be used. Where otherwise not specified, only participants with
222 non-missing data are included in analyses (i.e., complete-case analysis).

223 **1.15 Outliers**

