224 To ensure that statistical outliers do not have an undue impact on analyses of continuous
225 outcomes, change in continuous outcomes from baseline will be truncated to ± 3 standard
226 deviations based on the overall mean and standard deviation from both treatment groups
227 combined at 24 weeks. Truncation will occur after imputation, where applicable.

228 **1.16 Model Assumptions and Nonconvergence**

229 All model assumptions will be verified. If model assumptions are seriously violated, covariates
230 may be categorized or excluded, and a non-parametric approach, robust method, or
231 transformation may be considered. The proportional hazards assumption will be assessed by
232 visual inspection of Kaplan-Meier curves. If the proportional hazards assumption is seriously
233 violated, then an alternative approach, such as analysis of restricted mean survival time, may be
234 undertaken.

235 If a logistic regression models fail to converge, then covariates will be excluded, missing data
236 will not be imputed (where applicable), the confidence interval for the risk difference will be
237 estimated with the Newcombe method, and the *P* value for the treatment group comparison will
238 be calculated with Barnard's unconditional exact test.

239 **1.17 Revisions**

240 Owing to lower than anticipated final sample size, the following key changes were made to the
241 analysis plan after review of study data:

- 242 • Presence of epiretinal membrane has been removed as a covariate from all imputation
243 and regression models.
- 244 • Proportion of eyes with central VMT release and vitreopapillary traction (VPT) release
245 without rescue treatment at 24 weeks has been removed from the list of secondary
246 outcomes.
- 247 • A sensitivity analysis of confounding for the primary outcome has been removed.
- 248 • An alternative analysis method has been described for outcomes in which logistic
249 regression fails to converge.

250 In addition, treatment and subgroup effects from all logistic regression analyses will now be
251 summarized with a risk difference instead of a relative risk.

252 **References**

253 1. Dugel PU, Tolentino M, Feiner L, Kozma P, Leroy A. Results of the 2-Year Ocriplasmin
254 for Treatment for Symptomatic Vitreomacular Adhesion Including Macular Hole
255 (OASIS) Randomized Trial. *Ophthalmology*. 2016;123(10):2232-2247.

256 2. Stalmans P, Benz MS, Gandorfer A, et al. Enzymatic vitreolysis with ocriplasmin for

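### SAP 1.14 names only MCMC for all multiple imputation and states no model or conversion rule for the binary VMT-release outcome; the likely effect is small, and the remedy is a sequential binary imputation

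*SAP*

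**What the plan says.** - **Outcome and model (SAP 1.4).** "The primary outcome of central VMT release without rescue treatment at 24 weeks is a binary" "variable that is graded by the central reading center. Logistic regression will be used to test the" superiority hypothesis.
- **Who is imputed (SAP 1.4).** "Multiple imputation will be used to impute missing data for eyes lost to follow-up that did not" already have a documented release or rescue. An eye released before it was lost counts as a success, and a rescued eye counts as a failure.
- **Imputation model (SAP 1.4).** Treatment group "and VMT status at 1, 4, 12, and 24 weeks". Every one of these variables has two categories.
- **Method (SAP 1.14).** "For analyses using multiple imputation, the Markov chain Monte Carlo (MCMC") "method with 100 imputations will be used". No joint distribution, software or procedure is named. The same sentence governs the visual acuity imputation in SAP 1.5.1.
- **After imputation (SAP 1.15).** For continuous outcomes the plan gives a rule: "Truncation will occur after imputation, where applicable". Binary outcomes have no counterpart.
- **Safeguards.** SAP 1.16 says "All model assumptions will be verified. If model assumptions are seriously violated, covariates" may be categorized or excluded and other approaches considered. If a logistic model fails to converge, SAP 1.16 drops imputation and uses a Newcombe interval and Barnard's test. SAP 1.4 also plans a complete-case sensitivity analysis.
- Protocol 8.6 plans multiple imputation for the primary outcome but names no algorithm.

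**The concern.** MCMC named as an imputation method, with no distribution attached, is usually taken to mean data augmentation under a multivariate normal model. That suits letter scores. It does not suit a 0/1 variable that the plan treats as practically irreversible once it becomes 1.

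Under that reading, the imputed 24-week values are continuous, and someone must decide how to turn them into outcomes for the logistic model. The choice affects the primary estimate and is not written down. SAP version 2.0 was itself revised after study data had been reviewed and for a sample smaller than planned. A conversion rule left open at that stage would be chosen with data in view, and each imputed eye carries more weight in a smaller trial.

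The most obvious conversion, rounding at 0.5, also has a direction: it moves the two arms' imputed release rates toward each other.

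**Working it through.** **1. The plan's own figures.** For 60% v 30%, two-sided 5% and 90% power, the two-proportion formula with pooled variance and no continuity correction gives 56 per group, 112 in total (power 0.902), as in Protocol 8.3.2. All nine cells of Protocol Table 1 reproduce. Allowing for 10% loss, 112 × 1.1 = 123.2, or 124 when rounded up to a whole number of eyes, as stated; dividing instead, 112/0.9 = 124.4. Sample size is not at issue.

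**2. How many eyes are imputed.** Assumptions: 60% v 30% release; 10% loss; 35/65/90/100% of each arm's releases occurring by weeks 1/4/12/24. The documents do not give the final number of eyes, so three totals were tried (25 simulated trials each).

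| Total eyes | Mean eyes imputed | Draws exactly 0 or 1 | Draws outside 0 to 1 |
|---|---|---|---|
| 124 | 8.5 | 0% | 28% |
| 60 | 4.5 | 0% | 31% |
| 40 | 2.9 | 0% | 33% |

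The last two columns apply to multivariate-normal MCMC. A binary or categorical model sampled by MCMC returns only 0 or 1. One standard logistic routine rejected outcome values outside 0 to 1 but accepted fractions inside that range, so what happens without a conversion rule depends on the software.

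**3. Why rounding at 0.5 moves the arms together.** If an unreleased eye has conditional mean p and the model's residual SD is s, the chance that its draw rounds to 1 is Φ((p − 0.5)/s). This equals p only for one value of s:
- p = 0.05 (sham-like): s = 0.45/1.645 = 0.274
- p = 0.35 (PVL-like): s = 0.15/0.385 = 0.389

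The normal model uses one s for both arms. Any s between these two values overstates the sham rate and understates the PVL rate. At the midpoint, s = 0.331:
- sham: Φ(−0.45/0.331) = 0.087 instead of 0.05
- PVL: Φ(−0.15/0.331) = 0.325 instead of 0.35

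The two p values are round figures close to the true late-release rates in step 4. The midpoint s is illustrative.

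**4. Simulation.** Multivariate-normal data augmentation on treatment group and four statuses; cumulative release PVL 25/40/52/60% and sham 4/10/12/13% at the four visits; 25 or 62 eyes per arm; 150 replicates per setting. Late release in lost eyes, after rounding, was 8 to 9% against a true 4 to 6% (sham) and 27 to 32% against a true 32 to 36% (PVL). This agrees with step 3. Over these and a further set of runs (120 replicates, own assumed curves and loss pattern), the risk difference was too small by:
- 10% loss: about 0.1 to 0.9 points. In the further set, the shift at 25 eyes per arm could not be distinguished from zero.
- 20% loss: about 0.8 to 1.5 points.

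Runs with 30% sham release gave about 0.2 to 0.8 points over the loss rates tried, so the shift is smaller when sham release is higher.

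**5. Rough check on size.** Step 2 puts about 8.5/124 = 6.9% of eyes in the imputed set at 10% loss. Step 3's errors are 3.7 points (sham, upward) and 2.5 points (PVL, downward), 6.2 points together. Then 0.069 × 6.2 = 0.4 points, inside the simulated range.

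**6. Against sampling error.** SE of the risk difference = √[p₁(1 − p₁)/n + p₂(1 − p₂)/n].
- 60% v 13%, 62 per arm: √(0.00387 + 0.00182) = 7.5 points
- 60% v 13%, 25 per arm: √(0.00960 + 0.00452) = 11.9 points
- 60% v 30%, 62 per arm: √(0.00387 + 0.00339) = 8.5 points

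The largest shift at 10% loss is 0.9/7.5 = 0.12 SE. The largest at 20% loss is 1.5/7.5 = 0.20 SE.

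**7. The alternative.** Sequential binary imputation among unreleased eyes differed from the full-data result by 0 to −0.6 points at 20% loss, closer than rounded normal draws. At 10% loss the two methods were similar.

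**The case against.** The strongest objection is that the SAP never mentions normality. MCMC is a class of algorithms, and on a categorical model every draw is valid. A reader might infer that the plan imputes impossible values and that its logistic model cannot be fitted. The documents do not support that: the normal model is an inference from common usage, and even under it a rounding step makes the data usable. This objection stands, and the point is limited accordingly.

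A reader might also infer that the primary estimate is biased in any material sense. That does not follow either. The shift needs a normal model, rounding at 0.5 in particular, and assumed release and loss patterns. The larger figures use 20% loss, twice the planned rate, and the main release curves use 13% sham release where the trial was sized on 30%. Exposure is already limited, because releases and rescues seen before loss settle the outcome and the complete-case analysis would show whether imputation matters.

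The safeguards do not remove the gap. The fallback in SAP 1.16 is triggered by non-convergence, and outcome values that are not 0 or 1 are a different failure. The commitment to verify assumptions names no replacement imputation model. A sensitivity analysis does not define the primary one.

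One further objection concerns the remedy. With sham increments of 2 points by week 12 and 1 point by week 24, the chance of no sham release in the interval is 0.98²⁵ = 60% and 0.99²⁵ = 78% at 25 eyes per arm (29% and 54% at 62). A plain visit-by-visit logistic fit would often separate. This is correct, and the remedy must include a safeguard for it.

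**Conclusion.** Minor. SAP 1.14 applies one unspecified MCMC method to a binary primary outcome and does not say which imputation model is used or how non-binary draws would be handled. That much rests on the text alone.

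The consequence is conditional. If the normal form is used and draws are rounded at 0.5, the risk difference is attenuated by about 0.1 to 0.9 points at 10% loss and 0.8 to 1.5 points at 20%. These sizes depend on assumed release curves, loss timing and final sample size. They are at most about 0.2 standard errors and arise from few eyes (about 3 to 9 at 10% loss in step 2). A changed trial conclusion is unlikely.

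**What to change.** In SAP 1.14:
- Keep MCMC for the visual acuity imputation only.
- Impute VMT release with a sequential (monotone or fully conditional) logistic model that includes treatment group. At each missed visit, draw release among eyes not yet released, and keep released eyes as released. This matches the plan's own premise that re-attachment before 24 weeks is very unlikely.
- State in advance a penalized fit (for example Firth or a weak prior) for any visit with few or no releases in an arm.

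The cost is a short change of wording and slightly more programming. The drawback is that imputed values at sparse visits will depend partly on the chosen penalty. The sample size does not change, and the planned complete-case analysis stays as it is.
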